#### **Intramuscular Placebo**

Intramuscular placebo for injection vials were developed by Polymun Scientific Ltd; Austria, to match the active MVA-C investigational product. The placebo comprises a liquid formulation containing 20 mM Tris / 0.15 M NaCl (pH 7.5). Tris is used as buffer substance, sodium chloride for appropriate osmolality and hydrochloric acid for buffer pH adjustment.

Investigational medicinal product vials and bottles will be labelled and packaged according to regulatory requirements. The PI will ensure that staff administering the vaccines have been appropriately trained in the written procedures for delivery of the vaccines.

Investigators and trained members of the clinical team will be encouraged to administer the vaccine as soon as possible and within 2 hours of being removed from cold storage. The date and time of administration will be recorded in the Case Report Form (CRF) and medical notes.

Participants will receive I.M injections, and Ad4 or placebo administered orally, as described in the schedule of doses (Table 1). In Part I, 36 participants will receive Ad4CN54-Env in combination with CN54gp140, or MVA-CN54 and CN54gp140, whilst 12 participants will receive an oral placebo in combination MVA-CN54 and/or CN54gp140. Dosing will be at weeks 0 (Month 0), 12 (Month 3) and 24 (Month 6). The two best vaccine regimes from B-D (Ad4/gp140) and F-H (Ad4/MVA-C/gp140), provided they meet the pass criterion, will be expanded and 12 participants will be screened and enrolled for Part 2 of the study.

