#### **14.5.4 SAFETY OUTCOMES**

The AEs will be coded using MedDRA. If a participant reports the same event more than once then the worst severity and worst relationship to trial vaccine will be taken. Discrepancies between diary card and CRF reports will be queried by the monitor if unclear. It is assumed that the grade assigned by the clinician is more accurate, and this will be the grade reported in the tables. If the diary card grade is worse, this will be foot noted.

Safety outcomes will be reported overall with proportion and 95% confidence interval, and by group and time-point, and by relationship to study product, and method.

For the primary analysis of safety and tolerability endpoints (as defined in section 14.2), results will be expressed as a proportion with confidence interval.

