Part 2 is dependent upon Part 1 and is designed to study groups selected on performance in part 1 in an expanded number of subjects. Data from both stages will be combined for safety and immunological analyses.

3 Study Design

To identify an effective Ad4 based oral vaccine that promotes systemic and mucosal responses to the HIV-1 envelope glycoprotein. This study will adopt a two-part adaptive clinical trial.

The study will assist in rapidly screening the impact of different routes, combination regimes and boosting options to Ad4-EnvCN54, MVA-CN54 and CN54gp140 / MPLA, to augment systemic and mucosal antibody responses following initial priming with Ad4.

This is a phase I trial in healthy male and female participants. The study will enrol 48 participants to Part 1 (6 in each group) and 12 participants in Part 2. Recruitment will select potential participants who are willing to undergo serial blood draws. Additional participants may be enrolled to replace any early withdrawals.

The clinical trial was conducted at the NIHR Imperial Clinical Research Facility (ICRF) at Hammersmith Hospital, London.

3.1 Part 1

In Part 1, n=6 participants per group will be randomised to groups A-H (Table 1). This design varies the number of Ad4 administrations, from 1 to 3, combined with either CN54gp140 protein boosts (A-D) or co-administration of gp140 with MVA (E-H).

Arm 1 (Groups A-D): Depending on the allocation of groups, participants will receive Ad4-EnvCN54 or placebo orally, CN54gp140/MPLA, and placebo I.M injections at month 0 (Week 0), 3 (Week 12) & 6 (Week 24).

Arm 2 (Groups E-H): Depending on the allocation of groups, participants will receive Ad4-EnvCN54 or placebo orally, CN54gp140/MPLA and MVA-CN54 I.M injections at month 0 (Week 0), 3 (Week 12) & 6 (Week 24).

Groups A (gp140 alone) and E (MVA-CN54/CN54gp140 alone) will serve as control groups to assess the added benefit of the Ad4 vector. Each vaccine group (A-H) will be assessed for number of mucosal responders (mucosal antibody (nasal/rectal/genital) as measured by ELISA), and titre (mucosal and systemic) of antigen specific binding antibody.

Enrolment through to completion of the primary immunological assessment for each group will be 7 months.

3.2 Part 2

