The study hypothesis is that priming with an orally delivered mucosal replicating vector (Ad4) will significantly enhance the magnitude and durability of mucosal and systemic antibody responses to HIV-1 gp140 on boosting with recombinant protein, with or without co-administration of a non-replicating pox vector (MVA-C).

9 Study Populations

Four different study populations have been defined and listed according to their importance.

1. Safety population

Those participants who received at least one dose of experimental vaccine will be included in the safety population

2. Per-protocol (PP) population:

PP includes all participants randomised and immunised with all scheduled vaccinations, and who completed the trial with no major protocol deviations

3. Intention-to-treat (ITT) population:

ITT population includes all participants randomised and given at least one vaccination in the trial

4. Modified-Intention-to-treat (mITT):

mITT population includes all participants randomised and given at least one immunisation in the trial (including those participants whose sample collection occurred outside the allowed windows)

10 Study Endpoints

10.1 Primary Endpoints Measure(s) - Part 1 & Part 2

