12.2.2 Safety and Tolerability

Safety data analysis will be based on the safety population and procedure described in here is applicable for both part 1 and part 2.

The following table illustrates the schedule used in capturing and monitoring adverse events.

Visit		1	2	3	4	5	6	7	8	9	10	11
Study Month		M0			M3			M6				M12
Study Week		W0	W1	W4	W12	W13	W16	W24	W25	W26	W28	W48
Study Day		D0	D7	D28	D84	D91	D112	D168	D175	D182	D196	D336
Visit Windows (Days)	-90		±1	±2	(±7/+14)	±1	±2	(±7/+14)	±1	±2	±2	±14
Solicited Adverse Events		X ⁶	X		X ⁶	X		X ⁶	X			
Review Solicited AE on diary card			X			X			X			
Unsolicited Adverse events		X ⁶	X	X	X ⁶	X	X	X ⁶	X	X	X	
Serious adverse events		X	X	X	X	X	X	X	X	X	X	X

Information on three different types of adverse events/reactions were collected at various timepoints, particularly pre- and post- vaccination on the day, throughout the study namely the serious, solicited, unsolicited adverse events. Adverse events/reactions are categorised both in terms of the severity (graded 1-4) and relatedness to the IMP (unrelated, unlikely, possible, probable, and definitely related).

As part of the safety and tolerability aspect of the primary endpoint reporting, the following will be reported,

- The frequency and percentage of participants with vaccine-related serious adverse events (SAEs) throughout the study period
- The frequencies and percentages of participants with severe or greater (Grades 3-4) adverse reactions at each time point during the study will be reported.

In addition to that, the frequencies and percentages of all adverse events/reactions separately for solicited, unsolicited and in combination will be reported and grouped by time point (separately for each time points and for all time points combined), severity

(graded 1-4) and relatedness (unrelated, unlikely, possible, probable, and definitely related). Whenever possible results will be split between arm 1 and arm 2 in part 1.

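### The SAP safety population omits controls who had only oral placebo, and the one treatment split it names cannot show an Ad4 effect

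*SAP*

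**What the plan says.** **Population.** SAP 9: "Those participants who received at least one dose of experimental vaccine will be included in the safety population". SAP 12.2.2 applies this set in both parts: "Safety data analysis will be based on the safety population". In the same section 9, the ITT set is worded differently and needs only one vaccination.

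**Reporting.** SAP 12.2.2 gives frequencies and percentages by time point, severity and relatedness. The only treatment split it names is: "Whenever possible results will be split between arm 1 and arm 2 in part 1". It mentions no confidence interval. Safety Tables 2.1 and 2.2 are listed in SAP 18, but no shell is shown for them. Protocol 14.5.4 plans more: "Safety outcomes will be reported overall with proportion and 95% confidence interval, and by group and time-point". It also expresses the primary safety endpoints as a proportion with a confidence interval.

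**Exposure.** In Table 1, groups A and E (6 each) receive oral placebo alone at month 0 and their first active product at month 3. Protocol 11.1 states: "In Part I, 36 participants will receive Ad4CN54-Env in combination with CN54gp140, or MVA-CN54 and CN54gp140, whilst 12 participants will receive an oral placebo". SAP 3.1 says that A and E "will serve as control groups to assess the added benefit of the Ad4 vector".

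**Causality.** Protocol Table 4 classes every solicited event that starts within 7 days of a vaccination as an adverse reaction.

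**The concern.** The safety and tolerability of oral Ad4 is a primary objective, and protocol 7.8 says there were no clinical data for Ad4-EnvCN54. Because of the automatic 7-day rule, background symptoms after a capsule count as reactions whichever capsule was swallowed. Relatedness tables therefore cannot separate vaccine from background for these events. Only the rate in people given oral placebo can do that.

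The SAP weakens this comparison in two ways. Its population wording can exclude only controls, because every participant in B–D and F–H receives Ad4 on day 0. Its named split pools Ad4 and oral-placebo recipients within each arm. A team programming from the SAP alone could follow it exactly and produce no table that sets Ad4 beside oral placebo.

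**Working it through.** **1. The protocol's own count.** From Table 1, with 6 per group: Ad4 at month 0 in B, C, D, F, G, H = 6 × 6 = 36; oral placebo in A and E = 2 × 6 = 12. This reproduces the 36 and 12 in protocol 11.1.

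**2. Ad4 share by arm and dose (Table 1).**

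| Dose | Arm 1 | Arm 2 |
|---|---|---|
| 1 (month 0) | B, C, D = 18/24 | F, G, H = 18/24 |
| 2 (month 3) | C, D = 12/24 | G, H = 12/24 |
| 3 (month 6) | D = 6/24 | H = 6/24 |

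The shares are equal at every dose, with 36 Ad4 doses per arm in total. At doses 2 and 3 the arms differ only in MVA v intramuscular placebo (24 v 24).

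**3. What the arm split can show after dose 1.** No boost has been given. With event rate pA on Ad4 and p0 on oral placebo, each arm expects 0.75·pA + 0.25·p0, so the expected arm difference is 0 for any pA and p0. The documents give no rates. With assumed values:
- pA = 20%, p0 = 5%: 0.75 × 20 + 0.25 × 5 = 16.25% in both arms, hiding a 15-point difference.
- pA = 30%, p0 = 5%: 0.75 × 30 + 0.25 × 5 = 23.75% in both arms, hiding a 25-point difference.

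**4. Controls who leave with oral placebo only.** Inputs: 12 controls; 10–20% withdrawal (protocol 12.8.1); timing not given, so assumed even over 26 weeks.
- Expected number before week 12 = 12 × d × 12/26. At d = 0.10 this is 0.55; at d = 0.20 it is 1.11.
- Chance of at least one = 1 − (1 − d × 12/26)^12 = 43% and 69%.
- A constant hazard instead gives 0.57 to 1.17 and 44% to 71%. If every withdrawal fell before week 12, the expected number would be 12 × d = 1.2 to 2.4.

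**5. Effect of one such leaver.** Withdrawals before week 26 are replaced. Suppose one early leaver had an event and the replacement did not. Everyone dosed gives 1/13 = 7.7%; the SAP set gives 0/12.

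**6. Precision of the dose 1 contrast.** With no events, exact two-sided 95% upper limits are 9.7% for 0/36 and 26.5% for 0/12. A single arm with 0/24 gives 14.2%.

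**7. Who is in the placebo column later.** At dose 2, oral placebo goes to A, B, E, F = 24, of whom B and F = 12 had Ad4 earlier. At dose 3 it goes to A, B, C, E, F, G = 36, of whom B, C, F, G = 24 had Ad4 earlier. Only weeks 0–12 compare Ad4 with people who have never had it.

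**The case against.** **The protocol still governs.** A reader might infer that Ad4 is never set against placebo in this trial. The documents do not support that. Protocol 14.5.4 calls for safety by group, which puts A and E beside the Ad4 groups. The SAP does not revoke it, does not say that the arm split is the only one, and shows no safety shell. What stands is narrower: the SAP does not carry over the protocol's by-group reporting and intervals, and the split it does name cannot replace them.

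**The exclusion is inferred.** The protocol summary lists both placebos under Investigational Products, and protocol 10.1.1 treats day 0 as the first vaccination for everyone. A generous reading would therefore keep placebo-only participants. But SAP 9 uses one wording for ITT and a narrower one for safety, so the generous reading cannot be relied on. The text needs settling either way.

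**Replacement.** A reader might infer that the control group shrinks. Under protocol 12.8.1 and SAP 7 it normally does not, and the protocol expects most withdrawals to be for personal circumstances. This largely protects the denominator. It does not bring back the leaver's events.

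**The arm split has a use.** With equal Ad4 shares it is a fair contrast of MVA with intramuscular placebo at doses 2 and 3, so no further table is needed for that.

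**The trial is not sized for comparisons.** Protocol 14.3 says so, and neither document plans a safety test. This argues against a test, not against a descriptive table.

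**Conclusion.** The point holds as a wording defect in the SAP safety population and a mismatch between SAP 12.2.2 and protocol 14.5.4.

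The population defect is small: about one control at most under even withdrawal. It is one-sided by construction, and it rests on the plain reading of SAP 9 and on the assumed timing.

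The reporting gap matters more and needs no assumption beyond Table 1, because equal Ad4 shares leave the arm split unable to show an Ad4 effect. The rates in the dose 1 illustration are assumed; the zero expected arm difference is not. A reader might carry that arithmetic to doses 2 and 3 and expect equal rates in both arms. That does not follow: everyone then receives the protein boost and only Arm 2 receives MVA, so boost reactions enter and the arms can differ.

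The gap persists in Part 2, for which the SAP names no treatment split. If the SAP 3.2 fallback is used, A and D are expanded for greater assessment of safety, and both lie in Arm 1, so an arm split would not separate them.

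**What to change.** 1. In SAP 9, define the safety population as everyone given at least one dose of any study product, active or placebo, analysed by product received.
2. In SAP 12.2.2, report the safety endpoints by group A–H and time point in Part 1, and by expanded group in Part 2, with exact (Clopper-Pearson) 95% intervals. This carries out protocol 14.5.4, using the interval method already named in protocol 14.3. Keep the Arm 1 v Arm 2 split as the MVA contrast.
3. Add one descriptive table of oral Ad4 v oral placebo for weeks 0–12, before any boost (36 v 12 in Part 1, plus any replacements), with no test.
4. If Ad4 v oral placebo tables are also made for doses 2 and 3, label the placebo columns as including earlier Ad4 recipients (12 of 24 and 24 of 36).
5. Provide shells for Tables 2.1 and 2.2.

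Cost: SAP wording and table layout. No new data are needed.

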10.1.1 Immunogenicity

Antigen specific mucosal (nasal and rectal for all, cervico-vaginal for women, and semen for men,) antibody (ng/ml) responses two weeks after the final immunisation. Out of these, nasal is considered to be the site with primary importance.

10.1.2 Safety and Tolerability

- Proportion of participants with severe or greater (Grades 3-4) adverse

- reactions during the study
- Proportion of participants with vaccine-related serious adverse events (SAEs) throughout the study period

10.2 Secondary Endpoints Measure(s) – Part 1 & Part 2

10.2.1 Immunogenicity:

To assess the kinetics of immune responses elicited by each of the vaccine regimens:

Frequency of serum and mucosal binding antibodies to HIV CN54gp140 antigen measured by binding ELISA.

10.3 Exploratory Endpoints Measure(s) - Part 1 & Part 2

The following endpoints are measured as part of the exploratory analysis.

- Frequency and magnitude of HIV-gp140 specific B-cell-mediated responses in the systemic compartment measured by B-cell ELISPOT.
- Frequency, titre and avidity of serum binding antibodies to other HIV Env antigens (alternative clades) by ELISA or other assays.
- Frequency and titre of serum neutralising antibodies to homologous virus, and, if warranted a wider a panel of viruses representing different clades.
- Longevity of serum and mucosal responses at 12 months following final immunization
- Frequency and magnitude of HIV-specific T-cell mediated responses measured by T-cell and ICS (Intracellular Cytokine Staining).
- PBMC ex-vivo HIV susceptibility assay
- Measurement of CN54gp140 serum IgA responses over time
- Frequency and magnitude of T-cell chemokine and cytokine release following ex-vivo antigen stimulation quantified by Luminex.
- Epitope mapping of B- and T-cell responses
- Serum antibody responses to Ad4-EnvCN54 and MVA-CN54 as a marker of anti-vector immunity and vaccine “take”
- Ex vivo analysis of colorectal biopsies for activation markers by ICS (Part 2 only)
- Susceptibility of rectal biopsies to HIV-infection – infection assays

Durability of responses will also be determined by measurement of response at weeks 26 (visit 9) and 48 (visit 11) of the trial schedule

11 Data Transfers

Most of the data is held in Promasys® database maintained by the section of data management at the Surrey CTU except the results of various laboratory results which are collated and held by the laboratory manager at Imperial College London.

Laboratory manager at ICL will send the laboratory data held in spreadsheets to the data management team at Surrey CTU.

Once the SAP is finalised and signed off, SAS datasets held in Promasys database and spreadsheets received from Imperial laboratory will be transferred into a folder that is only accessible by the statisticians and a data transfer form is signed by both the data manager and the statistician to confirm the data transfer has been successfully undertaken.

12 Statistical Analysis

12.1 Responders

All mucosal and serum samples will be screened for antigen specific antibodies (IgG and IgA). The absolute levels of antibody in samples that are found to be positive will be determined using a standardised and quantitative ELISA developed in [name]'s laboratory at Imperial College London. In this sandwich capture ELISA, the Ab of interest is captured by the relevant target antigen and then detected using a labelled isotype specific secondary Ab. An estimate of the concentration of Ab in the sample is calculated by interpolation relative to a standard curve based on titration of purified human standards IgG or IgA captured by anti-human kappa/lambda-specific antibodies.

The number of 'responders' in each assay will be presented by time-point and group as a proportion with 95% confidence interval. A 'responder' will be defined as a participant in whom a response was detected in the immunogenicity sample taken two weeks after the final vaccination. A positive result will be defined relative to a pre-defined cut-off threshold value and assays will be validated using predefined thresholds based on the responses to positive and negative control stimuli. More information on the assay and definition of positive results will be supplied in the LAP. Titres of antigen specific antibodies will be described by time-point and group and compared using rank tests where appropriate.

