Group	N	Month 0	Month 3	Month 6																																					
A	6	Oral placebo	CN54gp140 +Oral placebo +I.M placebo	CN54gp140 +Oral placebo +I.M placebo																																					
B	6	Ad4-EnvCN54	CN54gp140 +Oral placebo +I.M placebo	CN54gp140 +Oral placebo +I.M placebo																																					
C	6	Ad4-EnvCN54	CN54gp140 + Ad4-EnvCN54 + I.M placebo	CN54gp140 +Oral placebo + I.M placebo																																					
D	6	Ad4-EnvCN54	CN54gp140 + Ad4-EnvCN54 +I.M placebo	CN54gp140 + Ad4-EnvCN54 +I.M placebo																																					
E	6	Oral placebo	CN54gp140 +MVA-CN54 +Oral placebo	CN54gp140 +MVA-CN54 +Oral placebo																																					
F	6	Ad4-EnvCN54	CN54gp140 +MVA-CN54 +Oral placebo	CN54gp140 +MVA-CN54 +Oral placebo																																					
G	6	Ad4-EnvCN54	CN54gp140 +MVA-CN54	CN54gp140 +MVA-CN54																																					

			+ Ad4-EnvCN54	+Oral placebo
H	6	Ad4-EnvCN54	CN54gp140 +MVA-CN54 + Ad4-EnvCN54	CN54gp140 +MVA-CN54 + Ad4-EnvCN54
	48			

Participants will be randomised for recruitment into groups A-H in Part 1. The number of Ad4-EnvCN54 administrations combined with either gp140 protein boosts (A-D) or co-administration of gp140 with MVA-CN54 (E-H) will vary. Groups A (CN54gp140 alone) and E (MVA-CN54/CN54gp140 alone) will serve as control groups to assess the added benefit of the Ad4 vector. Following completion of Part 1, each vaccine group (A-H) will be assessed for number of mucosal responders (mucosal antibody (rectal/genital/oral) as measured by ELISA), and titre (mucosal and systemic) of antigen specific binding antibody. The primary immunogenicity endpoint will be Week 26; Visit 9. The vaccine groups and regimes (one from B-D and one from F-H) that have the best positive response at this timepoint will be expanded in Part 2 of the study.

Based on data from the MUCOVAC2 study, in which participants received 3 intramuscular doses of CN54gp140 with GLA-AF adjuvant, we anticipate that there will be no mucosal responders in group A (although there will be detectable systemic IgG responses). Enrollment through to completion of the primary immunological assessment for each group will be 7 months.

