## 7.6 CLINICAL STUDY DESIGN

To identify an effective Ad4 based oral vaccine that promotes systemic and mucosal responses to the HIV-1 envelope glycoprotein, our group will adopt a two part adaptive clinical trial. The study will assist in rapidly screening the impact of different routes, combination regimes and boosting options to Ad4-EnvCN54, MVA-CN54 and CN54gp140 / MPLA, to augment systemic and mucosal antibody responses following initial priming with Ad4.

The study will enrol 48 participants to Part 1 and 12 participants in Part 2. Recruitment will select potential participants who are willing to undergo serial blood draws. Additional participants may be enrolled to replace any early withdrawals.

**In Part 1**, n=6 participants per group will be randomised to groups A-H (Table 1). This design varies the number of Ad4 administrations, from 1 to 3, combined with either CN54gp140 protein boosts (A-D) or co-administration of gp140 with MVA (E-H). Groups A (gp140 alone) and E (MVA-CN54/CN54gp140 alone) will serve as control groups to assess the added benefit of the Ad4 vector. Each vaccine group (A-H) will be assessed for number of mucosal responders (mucosal antibody (rectal/genital/nasal) as measured by ELISA), and titre (mucosal and systemic) of antigen specific binding antibody. Based on data from the MUCOVAC2 study, in which participants received 3 intramuscular doses of CN54gp140 with GLA-AF adjuvant, we anticipate that there will be no mucosal responders in group A (although there will be detectable systemic responses). Enrolment through to completion of the primary immunological assessment for each group will be 7 months.

**In Part 2**, the best regimes from A-D (Ad4-EnvCN54/CN54gp140) and E-H (Ad4-EnvCN54/MVA-CN54/CN54gp140) will be expanded to n=12 (additional n=6) in Part 2. Immune responses at the Primary Immunogenicity Endpoint (Week 26) will be analysed. Selection will be based on total number of responders. In the event that more than one group has the same number of responders, mucosal antibody titre will be used to rank groups to determine which to take forward to Part 2. Should mucosal titers be indistinguishable between groups, then serum antibody levels will be taken into consideration in the selection of groups to progress to Part 2.

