**Table 7: Sample Size**

Number of “responders”	Proportion if n=6	95% confidence interval 
0	0%	0 – 39%
1	17%	0 – 64%
2	33%	4 – 78%
3	50%	12 – 88%
4	67%	22 – 96%
5	83%	36 – 100%
6	100%	54 – 100%

 Clopper-Pearson method (suitable for small sample sizes)

It is difficult to give an estimate of the power of group comparisons using quantitative antibody titre outcomes at this stage as this is dependent on the number of responders.

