Missing data will not be imputed. Where they occur, in the parametric analysis, they will be assumed to be missing at random, so that likelihood-based analyses (GLMM) will be considered robust. Case deletion will be automatic for non-parametric methods.

16 Interim analysis

No interim analyses are planned for this study.

17 Statistical software

Both SAS® version 9.4 and STATA IC version 16 will be used in the analysis and quality checking processes.

18 List of Tables

Table 1.1 – Part 1 - Primary Endpoint – Immunogenicity

Table 1.2 – Part 2 - Primary Endpoint – Immunogenicity

Table 2.1 – Part 1 - Primary Endpoint - Safety

Table 2.2 – Part 2 - Primary Endpoint - Safety

Table 3.1 – Part 1 – Secondary Endpoints

Table 3.2 – Part 2 – Secondary Endpoints

Table 4.1 – Part 1 – Exploratory Endpoints

Table 4.2 – Part 2 – Exploratory Endpoints

Summary Statistics 1.1 – Part 1 – Mucosal Response
Summary Statistics 1.2 – Part 2 – Mucosal Response

Summary Statistics 2.1 – Part 1 – Systemic Reponses
Summary Statistics 2.2 – Part 2 – Systemic Reponses

Summary Statistics 3.1 – Part 1 – Exploratory Endpoints
Summary Statistics 3.2 – Part 2 – Exploratory Endpoints

Summary Statistics 4.1 – Part 1 - Demographics
Summary Statistics 4.2 – Part 2 - Demographics

Summary Statistics 5.1 – Part 1 - Vital Signs
Summary Statistics 5.2 – Part 2 - Vital Signs

Summary Statistics 6.1 – Part 1 - Medical History
Summary Statistics 6.2 – Part 2 - Medical History

Summary Statistics 7.1 – Part 1 - Lab Parameters
Summary Statistics 7.2 – Part 2 - Lab Parameters

Example tables

Table 1.1a – Primary endpoint - Part 1 – Immunogenicity - Mucosal antibody responses at 26 weeks (numerical)

	Group	Arm 1				Arm 2				Kruskal-Wallis test p-value
		A	B	C	D	E	F	G	H	
IgG										
	N									
Nasal (ng/ml)	Median (IQR)									
Rectal (ng/ml)	Median (IQR)									
Cervico-vaginal (ng/ml)	Median (IQR)									
Semen (ng/ml)	Median (IQR)									
IgA										
	N									
Nasal (ng/ml)	Median (IQR)									
Rectal (ng/ml)	Median (IQR)									
Cervico-vaginal (ng/ml)	Median (IQR)									
Semen (ng/ml)	Median (IQR)									

Table 1.1b – Primary endpoint - Part 1 – Immunogenicity –Multiple comparison post-hoc tests following Kruskal-Wallis test*

Comparison	IgG					IgA			
	Nasal	Rectal	Cervico-vaginal	Semen		Nasal	Rectal	Cervico-vaginal	Semen
	p-value	p-value	p-value	p-value		p-value	p-value	p-value	p-value
A vs B									
A vs C									
A vs D									
B vs C									
B vs D									

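### The SAP gives a screen-negative sample no titre value, so read literally the mucosal titre rank tests use responders only and would probably lose control group A

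*SAP*

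**What the plan says.** **Measurement.** SAP section 12.1, and Protocol section 14.5.2 in the same terms, screens every mucosal and serum sample. It then says: "The absolute levels of antibody in samples that are found to be positive will be determined using a standardised and quantitative ELISA". The definition of a positive result is left to the Laboratory Analysis Plan (LAP).

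**Missing values.** SAP section 15 has three rules: "Missing data will not be imputed"; in the parametric analysis "they will be assumed to be missing at random"; and "Case deletion will be automatic for non-parametric methods". Neither the SAP nor the Protocol assigns a value (zero, a detection limit or a lowest rank) to a sample that was collected and screened negative.

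**Analysis.** For Part 1, SAP section 12.2.1.1 plans Kruskal-Wallis tests across the eight groups for each mucosal site and isotype, followed by Dwass-Steel-Critchlow-Fligner (DSCF) pairs. For Part 2, section 12.2.1.2 plans a mixed model, with the rank test as the fallback for severely skewed data. In both parts, section 12.2.1 also plans Fisher's exact test on responder status.

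**Controls.** SAP section 3.1 says that groups A and E "will serve as control groups to assess the added benefit of the Ad4 vector". Protocol section 7.6 states: "we anticipate that there will be no mucosal responders in group A".

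**The concern.** If only positives receive a concentration, and absent concentrations are deleted, the titre analysis conditions on being a responder. Response occurs after vaccination and is what the regimens are meant to change, so the groups entering the rank test are no longer the groups as allocated. Such a test cannot see a difference in response rate. It sees only differences in height among those who responded.

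The control suffers most. A group with no responders has no values, so the comparisons that should show what Ad4 priming adds to mucosal titre cannot be made. Medians mislead in the same way: a regimen with one high responder out of six could show a higher median than one with six moderate responders.

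In Part 2, a titre that is absent because it fell below the cut-off is absent because of its own unobserved value. The missing-at-random assumption does not plausibly cover that.

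**Working it through.** **1. The plan's own figure.** No power is stated for the rank tests. The nearest figure is Protocol Table 7, row 0/6, the result anticipated for group A, given as 0 to 39% by Clopper-Pearson. The two-sided 95% upper limit is 1 − 0.025^(1/6) = 45.9%. The printed 39% matches a one-sided limit, 1 − 0.05^(1/6) = 39.3%, or the Wilson limit, 39.0%. The other six rows reproduce as two-sided Clopper-Pearson. This discrepancy is separate and does not affect the present point.

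**2. What literal application does to group A.** With n = 6 and true response rate p, the chance of no positive sample is (1 − p)^6:

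| p | 0 | 5% | 10% | 20% |
|---|---|---|---|---|
| P(0 of 6) | 100% | 74% | 53% | 26% |

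When A is empty, Kruskal-Wallis falls from 8 groups (7 df) to 7 (6 df). Of the 8 × 7 / 2 = 28 pairs, the 7 involving A cannot be computed. Table 1.1b lists all seven.

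**3. What becomes testable if negatives are kept as ties at a floor.** Take A at 0/6 against another group at k/6. For k = 6 the rank sums are 21 and 57. Uncorrected, H = (12/(12 × 13)) × (21²/6 + 57²/6) − 3 × 13 = 8.308. The tie correction is 1 − (6³ − 6)/(12³ − 12) = 0.878, so H = 9.466. The DSCF p-value refers √(2H) to the studentized range for 8 groups.

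| k | H | Exact Wilcoxon p, unadjusted | DSCF p |
|---|---|---|---|
| 4 | 5.228 | 0.061 | 0.30 |
| 5 | 7.174 | 0.015 | 0.13 |
| 6 | 9.466 | 0.002 | 0.044 |

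With negatives deleted, none of these rows exists.

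**4. Simulated rejection by the overall Kruskal-Wallis test.** Assumptions, none taken from the documents except the expectation of zero in A: eight groups of 6; response 0% in A and E; one common rate in the six Ad4 groups; equal normal log titres among responders; alpha 0.05 (the SAP states none); at least 3,000 runs. Values left after deletion are 36 × rate, out of 48.

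| Ad4 response | Values left | Negatives deleted | Negatives at floor | Fisher's exact, 8 groups |
|---|---|---|---|---|
| 40% | 14.4 | about 1% | about 30% | about 42% |
| 60% | 21.6 | about 2% | about 75% | about 91% |
| 80% | 28.8 | about 3% | about 99.8% | about 100% |

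The deletion column is low by construction. Responders have equal titres, so nothing is left to detect once negatives go. That is the point: the test is blind to response rate.

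**5. Sensitivity.** With Ad4 response at 60% and both controls at 5%, 10% or 20%, rejection is about 2% with deletion in each case, against about 57%, 44% and 25% with a floor. The loss does not require an empty control group. Over four other assumed response patterns the range was 1% to 3% against 29% to 99.9%. With every group at 50%, the floor test rejected in about 4%, so flooring does not inflate the error rate there.

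**6. The shells.** Table 1.1a has a median (IQR) column for group A beside the Kruskal-Wallis p-value. The mucosal summary shell asks for mean (SD) in ng/ml at week 0, before any vaccination, in every group. Both need values that section 12.1, read literally, does not produce.

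**The case against.** The strongest reply is that no sentence says a negative is entered as missing. Section 15 deals with missing data, and a sample that was collected, screened and found negative is not obviously missing. The shells suggest that the authors expected values for group A, and the LAP, which was not available, may settle it. This stands in part: deletion is what the stated rules yield when combined, not a declared intention. But the shells supply no rule, and the SAP refers to the LAP only for the assay and for what counts as positive. The documents conflict, and two analysts could follow them to opposite results.

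Several stronger readings are tempting and are not supported:

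- **That the Protocol confirms deletion.** Protocol section 14.3 says the power of titre comparisons is hard to estimate "as this is dependent on the number of responders". That is equally true with negatives at a floor, as the floor column in the working shows.
- **That the test of Ad4's added benefit is lost.** Fisher's exact test on responder status is in the primary analysis and keeps every sampled participant, including all of A. In the simulated scenarios it is at least as powerful as the floored rank test. It does discard magnitude, whereas the primary endpoint in SAP section 10.1.1 is a concentration. Serum is a different matter, since the Protocol summary expects detectable systemic IgG in group A.
- **That both controls contribute nothing.** The documents anticipate no mucosal responders in A only. Zero in E is an assumption of the simulation.
- **That one strong responder would beat six moderate ones in the test.** The medians could be ordered that way, but one value against six cannot give an exact two-sided Wilcoxon p below 2/7 = 0.29.
- **That Part 2 selection would be driven by this.** The Protocol selects first on number of responders. SAP section 3.2 first requires at least two participants above a rectal IgA threshold.

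It is also fair to say that this is an exploratory Phase I trial that disclaims statistical confidence about group differences.

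**Conclusion.** The point holds as a conflict within the SAP that decides who enters the primary mucosal titre analysis. Section 12.1 with section 15, applied as written, gives a responder-only comparison, probably with no values from group A, and in Part 2 a missing-at-random assumption that negatives would break. It cannot be said that the sponsor will delete negatives, because the shells point the other way.

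The size is about 1% to 3% rejection with deletion against about 30% to 99.8% with a floor. This rests on assumed response rates (0% in A and E, 40% to 80% elsewhere), equal titres among responders and alpha 0.05. An empty group A rests on an anticipated rate of zero, and becomes less likely as the true rate rises. The finding covers mucosal titre analyses only. It does not reach the responder analysis or group A's serum IgG.

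**What to change.** Add one paragraph to SAP sections 12.1 and 15:

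- A collected sample that screens negative or falls below the assay limit is not missing. It enters all rank tests and medians tied at one common lowest value.
- Missing status and case deletion apply only to samples not collected or not assayable.
- In the Part 2 model, negatives are treated as left-censored and not as missing at random; otherwise the rank test is used there.
- N is reported by site and isotype, and any titre summary limited to responders is labelled descriptive.

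The numerical floor (for example half the lower limit of quantification) does not affect the ranks, provided it lies below every positive value. A Tobit fit as a Part 2 sensitivity analysis is optional.

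The cost is one SAP paragraph and one data-derivation rule, with no new assays or visits.
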